3.3.2 Specific adverse event data collection

To assess specific and potentially serious adverse events that may be related to the interventions, we will collect data on the following:

3.3.3 Adverse Event Reporting

Any unexpected adverse events will be recorded and reported directly to the appropriate IRB shortly following the event per local protocol.

4. SAMPLE SIZE CALCULATION AND STATISTICAL ANALYSIS PLAN

4.1 Sample size calculation

The study has been powered to have at least 80% power for the primary outcome for Cohort 1 (seat belt use). Based on Sommers et al., 2013, we can likely expect the intervention to increase the percentage of subjects reporting seat belt use by15% on top of self-monioting alone. Using a 2-sample test of proportions, estimating 25% of the intervention participants and 10% of the control (SMS self-monitoring) report always seat beltuse, we would need around 100 subjects per group to show a significant difference between arms. Expecting 10% drop-out in the SMS 2-week run-in and 80% completing 8-week assessments, 300 enrolled in the ED should provide an analyzed sample of 216 (108 per arm).

4.2 Statistical analysis plan

4.2.1 General considerations

The statistical analyses and reporting will adhere to the CONSORT guidelines. All tests will be twosided, a p-value < 0.05 will be considered significant, and all confidence intervals will have 95% coverage. All analyses will be conducted on a modified intention-to-treat basis only including participants responding to at least one week of SMS assessments during the intervention period. The two groups will be compared in relation to baseline characteristics using descriptive statistics. The persons conducting the statistical analysis will be blinded to the randomized allocation. Groups will be designated as "A" and "B" until all pre-specified analyses are performed and shared with all authors.

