2.11 Allocation to Treatment

Participants in each cohort who meet run-in criteria will be randomized in a 1:1 ratio to either the SMS intervention or SMS self-monitoring in blocks of 4. The randomization will be stratified according to site (i.e. ED). An independent statistician will create the randomization list using a random number generator. The randomization list will be stored in an electronic database to be unblinded once trial enrollment and follow-up periods have been completed.

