2.13 SMS vehicle safety self-monitoring (i.e. assessment control)

Participants allocated to the control arm will simply continue to receive weekly SMS assessments related to their target risk behavior without receiving any feedback or goal support for 12 more weeks.

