2.14 Outcome Assessments & Blinding

The primary outcomes will be the percentage of participants in each treatment arm who report vehicle risks at week 8 (immediate effects) and week 14 (durable effects). Questions are the same as those used in screening. Participants will receive a text prompting them to log in to the secure web site to complete the 21-question survey which should take them no more than 10 minutes to complete. Research associates and investigators will be blinded to the allocation until outcome evaluation. It is not possible to blind subjects given the nature of the intervention. We do not expect any scenarios where emergency unblinding will be necessary.

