Appendix: SMS Interventions: Seat belt Safety

Day & Time	Incomin	Outroing
Day & Time Qualified Week 3,	g	Outgoing
Monday, 5pm		
Qualified		Congratulations [Name]! You have qualified to continue the SaVE Study For the next 6 weeks, we will help you set goals and provide you personalized feedback on your seat belt use We will check in next Sunday. Until then, take care
Week 3-8: Sunday, 3pm		
2 hours 2 hours	[Missing] x1 [Missing] x2 [Nonsen se]	Hi [_NAME_], it's the SaVE Study Team checking in How often have you been a passenger or driver in a car the past week? 0=never; 1=a few times; 2=most days; 3=every day We missed your response. Text us how often you have been a passenger or driver in a car the past week? You must be busy. We will check in next week We don't understand. Please text us a response option: 0=never; 1=a few times; 2=most days; 3=every day
1 hour	0 1,2,3 [Missing] x1	OK When in the car, how often did you wear a seat belt? 0=never; 1=a few times; 2=most of the time; 3=every time We missed your response. Text us how often you wore a seat belt
1 hour	[Missing] x2 [Nonsen se]	You must be busy. We will check in next week We don't understand. Please text us a response option: 0=never; 1=a few times; 2=most of the time; 3=every time
If Goal Not Set	3	[Posiitve Reinforcement Message]
	0,1,2	[Social Norms Message]
If Goal Set	Goal met Goal not met	[Goal Met Message] [Goal Not Met Message]
		Would you be willing to commit to a goal to wear a seat belt every time this week?
1 hour	[Missing] x1 [Missing]	We missed your response. Text us whether you'd be willing to set a goal?
1 hour	x2 [Nonsen se]	You must be busy. We will check in next week We don't understand. Please text us either yes or no
No Goal	No	[No Goal Roll Library Message]
Goal +	Yes	[Goal Reinforcement Message]
Random 2 days per week, 4pm		
lf goal -		[Seat belt Safety Info Message]
lf goal +		[Goal Reminder Message]

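### Every between-arm analysis, including the week-8 primary comparison, drops randomised participants who send no SMS reply in the intervention period, and no all-randomised analysis is planned

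*Combined protocol and SAP*

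**What the plan says.** Section 4.2.1 sets one analysis population: "All analyses will be conducted on a modified intention-to-treat basis only including participants responding to at least one week of SMS assessments", with replies counted over the intervention period. Section 2.11 places randomisation earlier: "Participants in each cohort who meet run-in criteria will be randomized in a 1:1 ratio". The condition is therefore met or failed after allocation.

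Section 4.2.2 (chi-squared test, then logistic regression) compares the randomised groups but names no other population. Section 4.2.3 imputes missing week-8 and week-14 outcomes from SMS values, and its sensitivity analyses change the imputation technique only. Section 4.2.4 adds no further set.

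The week-8 outcome does not come from the weekly SMS dialogue. Section 2.14 states: "Participants will receive a text prompting them to log in to the secure web site to complete the 21-question survey". Under section 2.15, the week-8 payment depends on passing the run-in and completing that survey, not on SMS replies after week 2.

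**The concern.** A filter applied after randomisation can break the balance that randomisation provides if passing it depends on arm and is related to the outcome. Here the second condition is easy to imagine, since people who stop engaging may well be those still at risk. The first needs care.

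In the seat belt appendix, feedback and goal requests follow a reply. After two missed prompts the week's dialogue closes with "You must be busy. We will check in next week". Feedback and goal requests therefore cannot cause someone never to reply.

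What remains is narrower. Section 2.14 concedes that "It is not possible to blind subjects given the nature of the intervention". Before any first reply the intervention arm is told "For the next 6 weeks, we will help you set goals and provide you personalized feedback on your seat belt use". It may also get safety information texts ("Random 2 days per week, 4pm"), if people with no goal set are sent them. Section 2.13 says that controls "will simply continue to receive weekly SMS assessments related to their target risk behavior without receiving any feedback or goal support". Zero reply could therefore differ by arm.

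Two consequences follow. The primary comparison is not between the groups as randomised, and nothing in the planned output would show whether the filter changed the result. In addition, a zero-replier who completes the web survey is discarded although the primary outcome was observed.

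**Working it through.** **Inputs from the documents** (section 4.1 unless noted): always-belt rates of 25% (intervention) and 10% (control); two-sided alpha 0.05 (section 4.2.1); at least 80% power; 300 enrolled, 10% lost in run-in, 80% completing week 8.

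**The plan's own figures reproduce.** With pooled variance and no continuity correction, n = [1.960·√(2·0.175·0.825) + 0.842·√(0.25·0.75 + 0.10·0.90)]² / 0.15² = 99.5, so 100 per arm. Attrition: 300 × 0.90 = 270 randomised (135 per arm); 270 × 0.80 = 216 analysed (108 per arm). Power is 83.1% at 108 per arm. The sample size is sound; the issue is the analysis population.

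**Size of the shift (illustration).** The documents give no zero-reply rate, so the exclusion shares are assumptions. Let b = 0.10 be the true always-belt rate in both arms (no effect), e the share excluded, and s the always-belt rate among those excluded. The rate after exclusion is (b − e·s)/(1 − e).

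| Excluded, intervention vs control | s = b | s = b/2 | s = 0 |
|---|---|---|---|
| 5% vs 5% | 0 | 0 | 0 |
| 10% vs 5% | 0 | 0.29 points | 0.58 points |
| 20% vs 5% | 0 | 0.99 points | 1.97 points |

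For example, the last cell is 0.10/0.80 − 0.10/0.95 = 0.1250 − 0.1053 = 1.97 points. The sign reverses if controls reply less.

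**Type I error**, by exact enumeration of the uncorrected chi-squared test, at s = 0:
- Everyone not excluded is observed: 5.35% for 10% vs 5% (n = 122 vs 128) and 7.71% for 20% vs 5% (n = 108 vs 128).
- 108 per arm observed: 5.46% and 7.63%, against 5.27% for the same test with no bias.

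The shift grows with the base rate. If the true always-belt rate were 25% in both arms, 20% vs 5% at s = 0 would give 0.25/0.80 − 0.25/0.95 = 4.9 points and about 13.4% rejection (normal approximation).

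**How much comes from discarding observed surveys.** Assume s = 0, 80% survey completion in each arm, and a share q of zero-repliers completing the survey. With those surveys restored, the observed rate is (0.8 − e·q)·[b/(1 − e)]/0.8, and the filter had dropped 135·e·q observed outcomes.

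| Excluded | q | Outcomes dropped | Shift with filter | Shift after restoring |
|---|---|---|---|---|
| 10% vs 5% | 25% | 3.4 vs 1.7 | 0.58 | 0.40 |
| 10% vs 5% | 50% | 6.8 vs 3.4 | 0.58 | 0.22 |
| 20% vs 5% | 25% | 6.8 vs 1.7 | 1.97 | 1.36 |
| 20% vs 5% | 50% | 13.5 vs 3.4 | 1.97 | 0.74 |

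Restoring the surveys removes only part of the shift. The rest is missing data, which the imputation has to handle.

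**Power of an all-randomised analysis** (pooled z test, 108 to 135 per arm, depending on what imputation recovers):
- No dilution, 25% vs 10%: 83.1% to 90.5%.
- 5% of the intervention arm at the control rate (0.95 × 25% + 0.05 × 10% = 24.25%): 79.8% to 87.9%.
- 10% at the control rate (23.5%): 76.1% to 84.8%.

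**Counting missing as risk, at 135 per arm:**
- 20% missing in both arms (20% vs 8%): 81.5%.
- 20% intervention vs 10% control missing (20% vs 9%): 73.0%.
- 10% vs 20% missing (22.5% vs 8%): 91.7%.

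**The case against.** The case for leaving the plan alone is that the rule is pre-specified, identical in both arms and easy to pass: everyone randomised has already replied during the run-in, and one reply in six weeks is enough. Analysts work with masked arm labels, which limits discretionary exclusion. The route to arm-dependence is thin. It rests on one introductory text and on information messages that the appendix does not clearly say are sent to people who have never replied. The control arm's texts after the run-in are not shown. In the 10% vs 5% case with the worst assumption about outcomes, type I error at 108 per arm rises only from 5.27% to 5.46%. The survey is prompted by text, the channel these people have ignored, so few may complete it. For those who do not, imputation has only baseline data and the run-in replies to work from.

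Most of this stands, and it limits the size of the problem. Exclusions may well be few, the direction is unknown, and 90% power is a ceiling that will not be reached in practice. Read literally, the rule also cannot apply to the screening and run-in percentages. None of this supplies an all-randomised comparison or justifies deleting an observed primary outcome. The run-in already screens for compliance before randomisation, where it does not bias the comparison, and the plan gives no reason for a second filter afterwards.

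**Conclusion.** The concern holds. The plan restricts every between-arm analysis by a post-randomisation condition and provides no analysis that would reveal its effect. The harm is probably small: 0 to 0.6 points for 10% vs 5% excluded and 0 to 2.0 points for 20% vs 5%, against a 15-point design difference, with type I error at most about 5.5% and 7.7% respectively. These figures assume no true effect, a 10% always-belt rate and exclusion rates that the documents do not give. The shift is nil if exclusions are balanced and similar, or if excluded people have the same outcome rate as the rest. The omission itself is certain; the size and direction of any bias are not. It should be fixed because the rule governs every comparison between arms and the remedy is cheap.

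**What to change.** In section 4.2.1, define the primary set as all randomised participants, analysed as allocated. For the week-8 outcome, state this order:

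1. Use every observed web survey.
2. Where there is none, apply the SMS rule in section 4.2.3 if usable SMS values exist.
3. Otherwise use the multiple imputation already named in section 4.2.3, drawing on baseline data and prior SMS, including run-in replies.

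Keep the set with at least one SMS week as a sensitivity analysis. Add missing-counted-as-risk as another; it should not be primary, because its power moves between 73% and 92% when missingness is unequal. Report zero-reply counts by arm, and how many of those participants completed the week-8 survey. State that the denominator for the SMS-completion outcome in section 3.1.3 is everyone randomised to intervention.

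The cost is SAP text, one imputation step and two sensitivity analyses, with no new data and no change in enrolment. The drawbacks are greater reliance on imputation for zero-repliers without a survey, and some dilution if they get no benefit. In the dilution cases above, power falls slightly below 80% if imputation adds nothing to 108 per arm.

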4.2.2 Primary Analysis

At baseline, all participants (based on screening criteria) all had the risk factor. At subsequent time points, participants are analyzed as having/not having the same risk factor by randomized group. For our primary analysis, we will examine the proportion of participants in each group (SMS intervention; assessment control) who report the risk behavior using a chi-squared test of proportions. We will then perform a logistical regression, entering any baseline attribute that has univariate association with the outcome in the final model. We will report the difference in percentage with primary outcomes as well as odds ratios (from logistical regressions) with 95% confidence intervals The α level is set at .05 for all statistical tests.

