2. TRIAL DESIGN

2.1 Overview

We propose to conduct 3 related randomized, controlled, parallel group, assessor-blind, superiority trials of 6-week text message interventions vs. SMS vehicle safety self-monitoring in young adult participants with risky vehicle behaviors. A total of 500 adult participants will be enrolled: 300 into Cohort 1 (seat belt); 100 into Cohort 2 (distracted driving); 100 into Cohort 3 (drink driving). Each SMS intervention will be desgined to target a single risk behavior. The study is powered to show a difference of 15% in the percentage of subjects reporting seat belt use at week 8. Other cohort trials (i.e. distracted driving, drink driving) and outcomes will be exploratory.

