Appendix: Screening Questions

Question	How old are you?	18 years old	19 years old	20 years old	21 years old
Code	age	0	1	2	3
Question	What is your sex?	Female	Male		
Code	sex	0	1		
Question	Are you Hispanic or Latino?	No	Yes		
Code	hisp	0	1		
Question	What is your race? (Select one or more responses.)	Black or African American	White	Asian	Other
Code	brace, wrace, asian, rother	0/1	0/1	0/1	0/1
Question	Are you currently enrolled in school?	No	Yes, High School	Yes, College	
Code	school	0	1	2	
	The following questions ask you to recall times you have been in a car over the past 2 weeks.				
Question	How often have you driven a car?	Never	A few times	Most	Every
Code	driver	0	1	days 2	day 3
Question	How often did you wear a seat belt when you drove a car?	Never	A few times	Most of the time	Always
Code	drive_seatbelt	0	1	2	3
Question	How often have you been a passenger in the front seat of a car?	Never	A few times	Most days	Every day
Code	pass_front	0	1	2	3
Question	How often did you wear a seat belt when you were a passenger in the front seat ?	Never	A few times	Most of the time	Always
Code	pass_seatbelt1	0	1	2	3
	How often have you been a passenger in the back seat of a car?	Never	A few times	Most days	Every day
	pass_back	0	1	2	3
	How often did you wear a seat belt when you were a passenger in the back seat?	Never	A few times	Most of the time	Always
	pass_seatbelt2	0	1	2	3
Question	How often did you type on your phone while you were driving and when the car was moving?	Never	A few times	Most of the time	Always
Code	distract	0	1	2	3
Question	Have you driven a vehicle within 3 hours after consuming 3 or more alcoholic drinks?	No	Yes		
Code	drinks	0	1		
	Thanks! Please hand the iPAD back to the Researcher.				

RA enters code: SAVE

Program displays which risks+

Script RA tells pt they are potentially eligible for study or thanks them for their time.

If eligible pt interested, RA asks the following:

Question	Do you have a personal cell phone with text messaging ?	No	Yes
Code	sms	0	1
Question	Do you plan to drive and/or ride in a vehicle in the next month?	No	Yes
Code	future	0	1
Question	Do you plan to change phone numbers in the next 3 months?	No	Yes
Code	phone	0	1

Logic If sms=0 or future=0 or phone=1, they are excluded.

RA either thanks them for their time or starts informed consent.

RA goes to WebDataXpress site

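### The primary Cohort 1 test is valid and meets its power target, but it leaves unused the graded baseline belt-use data that screening already collects

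*Combined protocol and SAP*

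**What the plan says.** Section 4.2.2 (Primary Analysis) starts from the remark "At baseline, all participants (based on screening criteria) all had the risk factor". It then compares the arms on the proportion "who report the risk behavior using a chi-squared test of proportions". A logistic regression follows, which takes in any baseline attribute found to have a univariate association with the outcome. The section reports a difference in percentages, and odds ratios from the regression. Baseline belt-use frequency is not named as a covariate in either step.

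The Appendix of screening questions grades belt use from never to always on four levels (coded 0 to 3). It asks "How often did you wear a seat belt when you drove a car", and the same for front-seat and back-seat travel. The typing item (`distract`) has four levels as well; the drink-driving item is yes/no. On the follow-up survey, Section 2.14 says "Questions are the same as those used in screening", and the 8-week and 14-week appendices bear this out for the belt and typing items.

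Section 4.1 sizes Cohort 1 as follows: "Using a 2-sample test of proportions, estimating 25% of the intervention participants and 10% of the control" reporting that they always wear a belt. This leads to about 100 per group, and 108 per arm expected in the analysis. Section 4.2.1 adds "All tests will be twosided, a p-value < 0.05 will be considered significant". Section 2.1 confines the powered claim to seat belts: "Other cohort trials (i.e. distracted driving, drink driving) and outcomes will be exploratory". Section 2.11 stratifies randomisation by ED only.

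**The concern.** The yes/no risk is constant at entry because eligibility makes it so. The measurement behind it is not constant. Someone who wore a belt on most trips is plausibly nearer to wearing it on every trip at week 8 than someone who never wore one. If so, baseline frequency predicts the outcome, and a comparison that ignores it has a larger standard error than it needs.

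Baseline belt use is also not balanced by design, since only ED is a stratification factor. Any chance difference between arms therefore passes straight into the headline difference in percentages. At stake are some avoidable type II error and some avoidable noise in the estimate for the one powered comparison.

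**Working it through.** **Inputs from the plan.** 10% versus 25% always belted at week 8; about 100 per arm required; 300 enrolled, 10% run-in loss, 80% completing week 8 (Section 4.1); two-sided 0.05 (Section 4.2.1); 1:1 allocation (Section 2.11).

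**Input not in the plan.** The strength of association between screening belt use and the week-8 outcome. It is assumed below and varied.

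**Step 1: reproduce the plan's figure.** With pooled rate 0.175, the size per arm is

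n = [1.96·√(2·0.175·0.825) + 0.8416·√(0.10·0.90 + 0.25·0.75)]² / 0.15² = (1.0532 + 0.4434)² / 0.0225 = 99.5, so 100.

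This matches. The analysed sample also matches: 300 × 0.9 × 0.8 = 216, or 108 per arm.

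**Step 2: power of the planned test.** Power = Φ[(0.15·√n − 1.0532) / 0.5268].
- n = 100: Φ(0.848) = 80.2%.
- n = 108: Φ(0.960) = 83.1%.

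**Step 3: baseline range that survives eligibility.** Score each Cohort 1 participant by the lowest belt frequency over the seat positions actually used. Anyone always belted in every position is not eligible, so three levels remain: never, a few times, most of the time.

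**Step 4: effective sample size.** If baseline explains a share R² of outcome variance within arms, use 108/(1 − R²) in Step 2. The requirement of 100 per arm falls to 100·(1 − R²).

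| R² (assumed) | Power at 108 per arm | n per arm for 80% |
|---|---|---|
| 0 | 83.1% | 100 |
| 0.02 | 83.9% | 98 |
| 0.05 | 85.0% | 95 |
| 0.10 | 86.9% | 90 |
| 0.15 | 88.7% | 85 |
| 0.20 | 90.5% | 80 |

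**Step 5: simulation.** 108 per arm, marginal rates held at 10% and 25%, three-level baseline with an assumed odds ratio (OR) per level. The chi-squared test is compared with a likelihood-ratio test of arm in a logistic model with the baseline score. There were 5,000 trials per setting for the first two baseline splits and 4,000 for the third.

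| Baseline split (never / few / most) | OR per level | Chi-squared | Adjusted | Gain (points) |
|---|---|---|---|---|
| equal thirds | 1.5 | 84.7% | 85.1% | 0.4 |
| equal thirds | 2 | 84.3% | 85.5% | 1.2 |
| equal thirds | 3 | 83.3% | 86.5% | 3.2 |
| equal thirds | 4 | 83.9% | 88.7% | 4.8 |
| 20/40/40 | 1.5 | 84.0% | 84.6% | 0.6 |
| 20/40/40 | 4 | 83.6% | 87.3% | 3.8 |
| 25/35/40 | 2 | 84.5% | 86.2% | 1.7 |
| 25/35/40 | 4 | 83.6% | 87.1% | 3.5 |
| 25/35/40 | 7 | 83.6% | 89.5% | 5.9 |

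With OR 1 there is no gain beyond simulation noise; one power figure has a standard error of about √(0.85·0.15/5000) = 0.5 points. Under the null with OR 3, rejection rates were 5.0% (chi-squared), 4.9% (adjusted logistic) and 4.7% (standardised risk difference). The adjusted model has the form that generated the data, so these gains are somewhat favourable to it.

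**Step 6: chance imbalance.** With the 25/35/40 split the score has SD 0.792, so the between-arm difference in means has SD 0.792·√(2/108) = 0.108. A deficit of more than 0.1 level in the intervention arm then has probability Φ(−0.1/0.108), about 18%. In simulated trials of that kind, chi-squared power was 78%, 73% and 72% at OR 2, 3 and 4; the adjusted test kept 86%, 85% and 87%. Imbalance in the other direction flatters the chi-squared test, and Step 2 averages over both.

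**The case against.** The case for leaving the plan alone is substantial. The chi-squared test is valid under randomisation, matches the sample-size calculation, and meets the stated power. All of that stands.

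The prognostic strength is assumed, and the protocol gives reasons why it may be low. Eligibility narrows the range. Section 2.10 expects enrolment and self-monitoring alone to shift behaviour before randomisation. The lowest-position score is noisy: a driver who is always belted but rode once unbelted in the back scores as never, and may be risk-free at week 8 just by not riding there. This stands too, and is why the low end of the gain is near zero.

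It can also be said that the plan already adjusts, since a strongly prognostic screening item would probably be picked up by the univariate rule. That is only a partial answer. The regression comes after the primary test, its covariates depend on the outcome data, and the difference in percentages is not tied to it.

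Three stronger readings are tempting and are not supported:
- A reader might infer that Cohort 1 is underpowered. Step 2 shows that it is not. The figures below 80% in Step 6 are conditional on an unlucky allocation; they are not the power of the design.
- A reader might put in a baseline-outcome correlation of 0.5 and claim a 9-point gain (83% to 92%). With the 25/35/40 split, even if every control success came from the top level, the control-arm correlation is at most 0.10·(2 − 1.15)/(0.792·0.30) = 0.085/0.2376 = 0.36. The split is an assumption, but nothing in the documents supports 0.5.
- A reader might extend the power argument to typing. Cohort 2 is exploratory, so the typing item has no bearing on the powered comparison.

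**Conclusion.** The point holds as one of efficiency and robustness, for Cohort 1. The primary test and headline difference leave out a prognostically plausible baseline measure that the trial already records. The expected gain from using it is about 0.5 to 6 points of power over the planned 83.1%, given assumed odds ratios of 1.5 to about 7 per level and the assumed baseline splits above. There is no gain if screening frequency does not predict week-8 use. Type I error is unaffected. The firmer benefit is that a chance imbalance in baseline belt use would no longer move the primary estimate unchecked. Nothing here makes the planned test wrong or the sample size inadequate. The change is worth making because it costs so little.

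**What to change.** In Section 4.2.2, before unblinding:
- **Cohort 1 primary analysis:** one logistic model with treatment arm and screening belt-use frequency, defined as the lowest frequency over seat positions actually used, with a stated rule for collapsing sparse levels.
- **Primary estimate:** the standardised (marginal) risk difference with a robust or delta-method 95% CI.
- **Sensitivity analysis:** the unadjusted chi-squared test and raw difference in percentages.
- **Existing regression:** replaced by this model, so that two overlapping adjusted analyses do not remain.
- **Week 14:** the same model.
- **Cohort 2:** the `distract` score may be used in the same way, labelled exploratory.
- **Cohort 3:** stays unadjusted for baseline, since its screening item is yes/no.

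Section 4.1 can stand, because its unadjusted calculation is then conservative. The cost is SAP wording and a few lines of code, with no extra participants or data. The downsides are that the primary result comes from a model instead of a 2×2 table, and that the three cohorts' primary tests differ slightly.

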2.2 Setting

The trial will be conducted at 4 hospital emergency departments in Pennsylvania. Additional sites might be recruited if needed.

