8.2 Screening & Enrollment

Enrollment at each site will be continuously monitored by the site investigator and the principal investigator. Each site will maintain a screening log including all participants who meet all eligibility criteria at that site. A standardized screening log will be kept using WebDataXpress, thus allowing for continuous updating of the screening log and will allow capture of all screening failures.

Enrollment will be competitive (i.e. without specific enrollment caps). Number of enrollments at each site will be shared with all sites on a monthly basis. Sites will be expected to complete all elements of the online screening and enrollment forms for each subject. In the case that a site continuously underperforms despite troubleshooting and feedback, the Investigators will evaluate whether enrollment will continue at that site.

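### Randomisation is stratified by ED, but the primary chi-squared test and risk-difference interval do not use ED; when EDs differ materially the analysis is somewhat conservative and forgoes a little precision

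*Combined protocol and SAP*

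**What the plan says.** Section 2.11 has participants in each cohort "randomized in a 1:1 ratio to either the SMS intervention or SMS self-monitoring in blocks of 4" and adds: "The randomization will be stratified according to site (i.e. ED". Section 2.2 gives the number of strata: "The trial will be conducted at 4 hospital emergency departments in Pennsylvania". It also says that "Additional sites might be recruited if needed". Stratum sizes are not fixed, because Section 8.2 says: "Enrollment will be competitive (i.e. without specific enrollment caps".

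Section 4.2.2 makes the primary comparison of proportions "using a chi-squared test of proportions". A logistic regression follows, "entering any baseline attribute that has univariate association with the outcome in the final model". On reporting, it says: "We will report the difference in percentage with primary outcomes as well as odds ratios (from logistical regressions) with 95% confidence intervals". ED is not mentioned in that section, either for the test, for the interval around the difference, or as a required covariate.

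Section 4.1 sizes Cohort 1 with the same two-sample comparison: 25% against 10% reporting that they always use a seat belt, about 100 per arm for at least 80% power, and 216 analysed (108 per arm). Section 2.1 calls the other two cohorts exploratory.

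**The concern.** Stratified blocks hold the arms close to balance within each ED, so differences between EDs contribute little to the difference between arms. The unstratified standard error is built from the overall proportions and treats that between-ED variation as noise in the comparison. If the rate of always using a belt differs between EDs, the nominal standard error exceeds the true one. Type I error then drifts below 5%, the interval covers slightly more than 95%, and some attainable precision is not used.

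The supportive logistic model does not settle this. ED enters it only if it passes a univariate screen, and whatever enters that model leaves the chi-squared test and the risk difference as they are.

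What is at stake is efficiency and a clean match between design and analysis in the one powered cohort. Validity is not threatened, since the error is on the conservative side.

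**Working it through.** **Inputs from the plan.** Rates of 25% and 10%, two-sided 5%, 80% power, 10% run-in loss and 80% completion (Sections 4.1 and 4.2.1); four EDs (2.2); 1:1 allocation in blocks of 4 by ED (2.11).

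**The plan's own figure.** With pooled proportion 0.175, the two-proportion formula gives

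n = [1.96·√(2·0.175·0.825) + 0.842·√(0.10·0.90 + 0.25·0.75)]² / 0.15² = (1.053 + 0.443)² / 0.0225 ≈ 100 per arm.

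The analysed sample is 300 × 0.90 × 0.80 = 216. At 108 per arm, z = (0.15·√108 − 1.053) / 0.527 = 0.96, so power is 83.1%. The stated size reproduces for the unstratified test.

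**Effect of stratifying, by formula.** With equal-sized EDs, the variance of the stratified difference relative to the unstratified one is

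1 − (between-ED variance in control + between-ED variance in intervention) / (0.09 + 0.1875).

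The documents give no ED rates, so every spread below is an assumption, averaging 10% in control and 25% in intervention.

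Worked case, moderate spread, evenly spaced. Control is 4, 8, 12 and 16%, with variance 0.0020. Intervention runs from 15 to 35%, with variance 0.0056. The ratio is 1 − 0.0076/0.2775 = 0.973, whose square root is 0.986. The unstratified half-width is 1.96·√(0.2775/108) = 9.94 points, and the stratified one is 9.94 × 0.986 = 9.80 points.

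| Assumed ED spread (control; intervention) | Half-width, unstratified → stratified | Narrower by |
|---|---|---|
| None | 9.94 → 9.94 | 0 |
| Mild (7–13%; 20–30%) | 9.94 → 9.90 | 0.3% |
| Moderate (4–16%; 15–35%) | 9.94 → 9.80 | 1.3% |
| Large (2–20%; 8–44%) | 9.94 → 9.52 | 4.2% |

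**Effect by simulation.** Each scenario had 200,000 trials: 270 randomised over four EDs in blocks of 4, with 20% random loss equal by arm. CMH is the Cochran-Mantel-Haenszel test by ED without continuity correction.

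| Spread | Power, chi-squared | Power, CMH | Difference (points) | Type I error, chi-squared | Coverage, unstratified interval |
|---|---|---|---|---|---|
| None | 84.14% | 83.91% | −0.23 | 5.0% | 94.8% |
| Mild | 84.34% | 84.25% | −0.09 | 5.0% | 94.8% |
| Moderate | 84.28% | 84.74% | +0.46 | 4.8% | 94.9% |
| Large | 84.81% | 86.53% | +1.72 | 4.6% | 95.4% |

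CMH holds type I error at about 4.9–5.0% throughout. The Mantel-Haenszel interval with Sato variance is the wider of the two in 57%, 44%, 19% and 2.5% of trials, in the order of the rows.

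**Costs.**
- With the usual 0.5 continuity correction, CMH power in Cohort 1 is 78.8% (none), 79.2% (mild) and 79.8% (moderate), below the 80% target.
- Cohorts 2 and 3 would analyse about 100 × 0.90 × 0.80 = 72 each. At the same assumed rates, CMH against chi-squared is 38.3% against 39.2% (none) and 38.5% against 39.2% (mild).
- With eight EDs of very unequal size and no ED difference, power is 83.7% against 84.2% at Cohort 1 size and 37.2% against 39.1% at 72 analysed. In 43% and 86% of trials respectively, some patients sit in an ED with only one arm represented and so drop out of the stratified test.

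**The case against.** The strongest reply is that nothing the plan promises is lost. Section 4.1 sizes the trial on the unstratified test, the figure reproduces, and simulated power of that test rises slightly as EDs diverge. A reader might infer that ignoring the strata puts the 80% target at risk; the documents do not support that. What is given up is a possible bonus.

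A reader might also infer that the interval is noticeably too wide whenever EDs differ. In principle any difference has some effect, but for mild differences type I error and coverage cannot be told from nominal, and the stratified interval is the wider one in 44% of trials. A gain near 2 points needs control rates of roughly 2–20% across EDs. Every participant has the risk behaviour at entry, and no document suggests how far EDs diverge afterwards.

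Nor is stratifying free. It costs a little power when EDs are alike, more when strata are small. A continuity-corrected version would do harm in Cohort 1. The modified intention-to-treat rule in 4.2.1 and the expected 20% loss also disturb exact balance within EDs.

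Finally, ED could enter the logistic model through its univariate screen. That is true, but it is not assured, and it would not change the primary test.

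These points limit the size of the issue. The mismatch between 2.11 and 4.2.2 remains.

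**Conclusion.** The point holds as a minor improvement. The primary test and interval do not use the strata that governed allocation and are somewhat conservative if EDs differ materially. For Cohort 1 the gain from stratifying is about nil for mild ED differences, about 0.5 points of power for moderate ones and about 2 points for large ones, with an interval 0.3% to 4.2% narrower. Planned power is not missed and the primary result would remain valid.

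These sizes rest on assumed ED rates averaging the plan's 10% and 25%, four EDs of similar size, and loss that is random and equal by arm.

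**What to change.** Before unblinding, amend Section 4.2.2 as follows.

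1. Make the Cohort 1 primary test a Cochran-Mantel-Haenszel test stratified by ED, stated to be without continuity correction.
2. Report the Mantel-Haenszel risk difference with a named stratified variance for its 95% interval, for example Sato. The test alone does not repair the interval.
3. Keep the unstratified chi-squared test as a supportive result.
4. Pool any ED with participants in only one arm, or with fewer than a stated minimum, including any added site, with the other EDs of the same study site (Pittsburgh area or Philadelphia). Pooling by city would not work, because one of the western EDs is in McCandless.
5. For the exploratory Cohorts 2 and 3, either stratify by the two study sites or keep the unstratified test, and say which.

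The cost is a few sentences and no new data, since ED is already needed for randomisation. The statistical price is about 0.2 points of power in Cohort 1 if EDs do not differ. At the size of Cohorts 2 and 3, stratifying by ED would cost up to about 1 point, and more if many small EDs are added.
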